#### **6.4.3. Blinding of the Sponsor**

Sponsor and sponsor-delegate staff will be blinded to participants' assigned study intervention, except for sponsor and sponsor-delegate-staff involved in the assignment or distribution of study intervention. Sponsor and sponsor-delegate staff who are not directly involved with the conduct of this study will prepare analyses and documentation containing unblinded data while the study is ongoing to support interactions with the DSMB.

#### **6.4.4. Breaking the Blind**

The IRT will be programmed with blind-breaking instructions. In case of an emergency, the investigator has the sole responsibility for determining if unblinding of a participant's treatment assignment is warranted. Participant safety must always be the first consideration in making such a determination. If the investigator decides that unblinding is warranted, the investigator should make every effort to contact the study medical monitor prior to unblinding a participant's treatment assignment unless this could delay further management of the participant. If a participant's treatment assignment is unblinded, Pfizer must be notified within 24 hours after breaking the blind. The date and reason that the blind was broken must be recorded in the source documentation and CRF.

The study-specific IRT reference manual and IPM will provide the contact information and further details on the use of the IRT system.

#### **6.5. Study Intervention Compliance**

The pharmacy will complete the Dose Calculation Worksheet which will be provided as part of the IPM. The use of the Dose Calculation Worksheet is preferred, but it does not preclude the use of an existing appropriate clinical site documentation system. The existing clinical site's documentation system should capture all pertinent/required information on the

preparation and administration of the dose. This may be used in place of the Dose Calculation Worksheet after approval from the sponsor and/or designee.

Compliance with the study intervention is defined as receiving 100% of the doses as specified per protocol.

#### **6.6. Dose Modification**

No dose modification is allowed.

#### **6.7. Continued Access to Study Intervention After the End of the Study**

No study intervention will be provided to participants at the end of their study participation. It is expected that participants will be treated as required with standard-of-care treatments, as advised by their usual care physician.

#### **6.8. Treatment of Overdose**

For this study, any dose of study intervention greater than the maximum dose of study intervention according to the protocol within a 24-hour time period will be considered an overdose.

There is no specific treatment for an overdose.

In the event of an overdose, the investigator/treating physician should:

1. Contact the study medical monitor within 24 hours.
2. Closely monitor the participant for any AEs/SAEs and laboratory abnormalities as medically appropriate and follow up until resolution, stabilization, the event is otherwise explained, or the participant is lost to follow-up (as defined in [Section 7.3](#)).
3. Document the quantity of the excess dose as well as the duration of the overdose in the CRF.
4. Overdose is reportable to the Pfizer only when associated with an SAE.
5. Obtain a blood sample for PK analysis as soon as overdose is identified but no later than 24 hours from the last over-dosed study intervention if requested by the study medical monitor (determined on a case-by-case basis).

Decisions regarding dose interruptions or modifications will be made by the investigator in consultation with the study medical monitor as needed based on the clinical evaluation of the participant.

#### **6.9. Prior and Concomitant Therapy**

All participants are required to maintain stable dosing of permitted prescribed and OTC medications for the duration of the study.

### 6.9.1. Prohibited During the Study

The following therapies are prohibited during the study:

- Any additional therapies to treat CeD.
- Other investigational agents, including biologic or non-biologic immunosuppressive or immunomodulatory therapies.
  - Washout period for chronic, systemic non-biologic immunosuppressive or immunomodulatory agents (eg, methotrexate, sulfasalazine, or corticosteroids such as prednisone, etc.) is 3 months prior to screening.
  - Washout period for biologic immunosuppressive or immunomodulatory agents (eg, adalimumab, etanercept, certolizumab) is 12 months prior to screening; except anti-severe acute respiratory syndrome coronavirus 2 monoclonal antibodies.
- Non-investigational systemic immunosuppressive and immunomodulatory therapies (eg, IV or oral corticosteroids). Corticosteroids administered topically or by inhalation or other ways may be allowed but should be discussed with medical monitor prior to enrollment in the study or initiation of new treatment.
- All vaccines between 4 weeks prior to dosing through 4 weeks from the last dose of study intervention; vaccines are permitted at all other times during the study.

### 6.9.2. Permitted During the Study

Hormonal contraceptives that meet the requirements of this study are allowed to be used in participants who are WOCBP (see [Appendix 4](#)).

HRT use by postmenopausal women is permitted if they meet requirements in [Appendix 4](#).

Any other medication that is considered necessary for the participant's welfare that is not expected to interfere with the evaluation of KAN-101 may be given at the discretion of the investigator and documented on the CRF.

In cases involving concomitant therapies whose predicted interference with KAN-101 is unknown to the investigator, Pfizer should be contacted for discussion.

Any medication (including over-the-counter or prescription medications, vitamins, and/or herbal supplements) that the participant receives after enrollment through the last study visit must be recorded on the CRF. Participants should report any changes to permitted medications during the study to the investigator as soon as they occur. Medication changes must be documented in the participant's record and CRF.

Participants being treated for IBS symptomology will be allowed to continue current treatment (eg, dicyclomine) unless the drug is specifically prohibited; participants should be

CONFIDENTIAL

on a stable dose for at least 4 weeks prior to entry and remain on a stable dose throughout the study.

Antidiarrheal (eg, loperamide), antiemetics (eg, metoclopramide or ondansetron), or acetaminophen may be used for symptomatic treatment if warranted unless the drug is specifically prohibited. These symptomatic treatments are optionally allowed as pre-treatment to study intervention administration at Day 4 and Day 7 at investigator discretion. If given at a study visit, use must be recorded on the CRF.

#### **6.9.3. Rescue Medicine**

There is no rescue therapy to reverse AEs observed with KAN-101; standard medical supportive care, such as antiemetics (eg, metoclopramide or ondansetron), may be provided to manage AEs.

### **7. DISCONTINUATION OF STUDY INTERVENTION AND PARTICIPANT DISCONTINUATION/WITHDRAWAL**

#### **7.1. Discontinuation of Study Intervention**

It may be necessary for a participant to permanently discontinue study intervention. Reasons for permanent discontinuation of study intervention include the following:

- An AE that requires permanent discontinuation of study treatment\*;
- Noncompliance with the protocol;
- Investigator decision;
- Participant becomes pregnant;
- Participant death;
- Participant lost to follow-up;
- Termination of the study by the sponsor;
- Voluntary withdrawal of consent by the participant.

\* Note: AEs leading to the discontinuation of study intervention will be followed until resolution, stabilization, the event is otherwise explained, or the participant is lost to follow-up.

Note that discontinuation of study intervention does not represent withdrawal from the study. If study intervention is permanently discontinued, the participant should remain in the study to be evaluated for safety. See the SoA for data to be collected at the time of discontinuation of study intervention and follow-up for any further evaluations that need to be completed.

In the event of discontinuation of study intervention, it must be documented on the appropriate CRF/in the medical records whether the participant is discontinuing further

CONFIDENTIAL

receipt of study intervention or also from study procedures, further study follow-up, and/or future collection of additional information.

Participants who withdraw from treatment and do not receive 3 full doses should not undergo GC, have plasma samples taken for IL-2 on Day 15, Day 29, and Day 42, or receive a second EGD with biopsy.

#### **7.1.1. Liver Injury**

A participant who meets the criteria as described in [Appendix 6](#) will be withdrawn from study intervention.

#### **7.1.2. Pregnancy**

Pregnancy tests are conducted as specified per the [SoA](#) and administration of study intervention or 2-week GC will only be initiated in the presence of a negative pregnancy test.

If a participant is confirmed to be pregnant (see [Section 8.3.6](#)) during any visit, conducting of GCs and further dosing with study intervention will be discontinued immediately and permanently.

[Section 8.4.5.1](#) describes the follow-up activities if a participant meets EDP criteria.

#### **7.1.3. COVID-19**

If a participant has COVID-19 during the study, this should be reported as an AE or SAE (as appropriate) and appropriate medical intervention provided.

It is recommended that the investigator discuss temporary or permanent discontinuation of study intervention with the study medical monitor.

#### **7.1.4. Temporary Discontinuation**

In cases where a temporary discontinuation or dosing interruption is required, the total infusion should be completed within 6 hours of thawing the drug product. Any temporary discontinuations or interruptions of study intervention should be documented in the CRF.

See [Appendix 9](#) for detailed guidance regarding infusion administration interruptions due to IRR.

### **7.2.1. Withdrawal of Consent**

Participants who request to discontinue receipt of study intervention will remain in the study and must continue to be followed for protocol -specified follow-up procedures. The only exception to this is when a participant specifically withdraws consent for any further contact with them or persons previously authorized by the participant to provide this information. Participants should notify the investigator in writing of the decision to withdraw consent from future follow-up, whenever possible. The withdrawal of consent should be explained in detail in the medical records by the investigator, as to whether the withdrawal is only from further receipt of study intervention or also from study procedures and/or posttreatment study follow-up, and entered on the appropriate CRF page. In the event that vital status (whether the participant is alive or dead) is being measured, publicly available information should be used to determine vital status only as appropriately directed in accordance with local law.

### **7.3. Lost to Follow-Up**

A participant will be considered lost to follow-up if the participant repeatedly fails to return for scheduled visits and is unable to be contacted by the study site.

The following actions must be taken if a participant fails to return to the clinic for a required study visit:

- The site must attempt to contact the participant and reschedule the missed visit as soon as possible. Counsel the participant on the importance of maintaining the assigned visit schedule, and ascertain whether the participant wishes to and/or should continue in the study;
- Before a participant is deemed lost to follow-up, the investigator or designee must make every effort to regain contact with the participant (where possible, 3 telephone calls and, if necessary, a certified letter to the participant's last known mailing address or local equivalent methods). These contact attempts should be documented in the participant's medical record;
- Should the participant continue to be unreachable, the participant will be considered to have withdrawn from the study.

## **8. STUDY ASSESSMENTS AND PROCEDURES**

### **8.1. Administrative Procedures**

The investigator (or an appropriate delegate at the investigator site) must obtain a signed and dated ICD before performing any study-specific procedures.

Study procedures and their timing are summarized in the SoA. Protocol waivers or exemptions are not allowed.

Adherence to the study design requirements, including those specified in the SoA, is essential and required for study conduct.

All screening evaluations must be completed and reviewed to confirm that potential participants meet all eligibility criteria. The investigator will maintain a screening log to record details of all participants screened and to confirm eligibility or record reasons for screening failure, as applicable.

Every effort should be made to ensure that protocol-required tests and procedures are completed as described. However, it is anticipated that from time to time there may be circumstances outside the control of the investigator that make it unfeasible to perform the test. In these cases, the investigator must take all steps necessary to ensure the safety and well-being of the participant. When a protocol-required test cannot be performed, the investigator will document the reason for the missed test and any corrective and preventive actions that they have taken to ensure that required processes are adhered to as soon as possible. The study team must be informed of these incidents in a timely manner.

For samples being collected and shipped, detailed collection, processing, storage, and shipment instructions and contact information will be provided to the investigator site prior to initiation of the study.

The actual collection times of blood sampling may change. Additional blood samples may be taken for safety assessments at times specified by the sponsor or sponsor's designee, provided the total volume taken during the study does not exceed 550 mL within 60 days.

### **8.1.1. Telehealth Visits**

Telehealth visits may be used to assess participant safety and collect data points. Telehealth includes the exchange of healthcare information and services via telecommunication technologies (eg, audio, video, videoconferencing software) remotely, allowing the participant and the investigator to communicate on aspects of clinical care, including medical advice, reminders, education, and safety monitoring. Assessments that may be performed during a telehealth visit are described in the [SoA](#).

Study participants must be reminded to promptly notify site staff about any change in their health status.

## **8.2. Efficacy Assessments**

Efficacy assessments are performed at times specified in the [SoA](#).

### **8.2.1. Gluten Challenge**

All eligible, enrolled participants that received all three doses of study intervention will undergo a 2-week GC at starting Day 15.

- Participants are required to fast for at least 6 hours (or overnight), except for water and any medications they might have previously been prescribed, prior to GC. This pertains to both the study clinic visit during which the GC is performed (see [SoA](#)) and the at-home GC.
- At the Day 15 study visit, a qualified staff member will prepare the GC.
- Participants will consume 9g of gluten protein PO in the clinic and the participant will be observed for at least 4 hours to monitor for hyperacute reactions requiring medical treatment and collection of biomarker samples.
- Materials will be sent home with the participant to complete the GC daily for the next 13 days.

Completion of the GC is defined as consumption of the entirety of the 9g GC within approximately 15 minutes.

- At the Day 15 visit, participants will consume the GC on site under the observation of site staff. Participants will complete the remaining days of GC at home and document the completion of the GC via the eDiary.

Compliance with the GC is defined as completion of all 14 days of the GC. Only participants fully compliant with the GC may be analyzed as part of the PPS (see [Section 9.3](#)).

Only participants who have completed at least 7 days of GC should undergo the second EGD with biopsy. For participants who:

- Continue in the study, the EGD with biopsy will take place at the Day 29 visit (see [SoA](#)).
- Discontinue early, the EGD with biopsy will take place at the ET visit (see [SoA](#)).

Any symptoms associated with the GC should be recorded as AEs (see [Section 8.4](#)). Any AEs associated with the GC study assessment are separate to AEs related to study intervention (KAN-101/placebo).

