#### Objectives, Endpoints, and Estimands:

Objectives	Endpoints	Estimands
Primary:	Primary:	Primary:

Assess the ability of KAN-101 to attenuate gluten challenge (GC)-induced changes in duodenal histology as measured by changes in villus-height:crypt depth (Vh:Cd) ratio after a 2-week GC.

	

Changes from baseline in Vh:Cd ratio as assessed by esophagogastroduodenoscopy (EGD) with biopsy after 2-week GC (at Day 29)

	
Estimand 1: The primary estimand is the hypothetical estimand, which estimates the treatment effect of KAN-101 vs placebo for change from baseline in the ratio of Vh:Cd under the scenario of no intercurrent events. It includes the following 5 attributes:
 

Population: Participants who receive all 3 doses of study intervention and complete at least 7 days of GC.

Variable: the ratio of Vh:Cd change from baseline at Day 29.

Treatment conditions: KAN-101 or placebo.

Intercurrent Events: Prohibited medication. All data collected after any intercurrent events will be excluded.

Objectives	Endpoints	Estimands
		
 
• Population level summary: The LSM difference of the change from baseline in the ratio of Vh:Cd between KAN-101 and placebo.
 

Secondary:	Secondary:	Secondary:

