**Table 1. Schedule of Assessments**

Abbreviations used in this table may be found in Appendix 12 .	Scr.	Treatment Period				Gluten Challenge (Day 15 to 28)			Biopsy	FU	ET	Notes
Visit Identifier	V1	V2	V3	V4	V5	V6	V7	V8	V9	ET		
 
Day relative to start of study intervention (Day 1).
 
See Section 8.4.3 for follow-up AE and SAE assessments.
 
D16 and D21 are phone call visits (See Section 8.1.1) for collection of AEs and concomitant medications.
 

Type (Site or Phone Call)	Site	Site	Site	Site	Site	Phone	Phone	Site	Site	Site		
Study Day (D)	Up to -42 days	D1	D4	D7	D15	D16	D21	D29	D42	ET		
Visit Window (days)					+2	±2	+3	+3				
Prior/concomitant meds/procedures, incidental gluten exposure	X	X	X	X	X	X	X	X	X			
 
See Section 6.9 for additional information.
 
Incidental gluten exposure checked daily; entered into eDiary and reviewed at study visits.
 

EGD with biopsy (approx. 6 duodenal biopsies)	X							X		X		
 
EGD should only be performed after the participant has qualified with all other inclusion/exclusion criteria.
 
For rescreening, EGD does not need to be repeated if 1) <3 months have elapsed from last screening assessment, 2) the participant has continued GFD and 3) the participant has not undergone a GC.
 
Only participants who have completed all 3 doses of study intervention and at least 7 days of GC should undergo EGD with biopsy at D29 or at ET visit (if participant discontinues prior to D29).
 

PGIS		X			X			X	X	X		
 
Day 1 PGIS should be completed pre-dose (at least 5 minutes prior to infusion).
 

PGIC					X			X	X	X		
GC					D15-28 daily							
 
GC completed in clinic on D15 and at home for the next 13 days (D16 to D28).
 
Participants who withdraw from treatment and do not receive 3 full doses should not receive GC.
 

CDSD v2.1	To be completed daily											
 
PRO (CDSD® v2.1) will be completed via eDiary for at least 7 consecutive days during screening.
 
For re-screening: CDSD v2.1 only needs to be repeated if >3 months have elapsed from end of last PRO administration.
 

CONFIDENTIAL

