### 9.3. Analysis Sets

For purposes of analysis, the following analysis sets are defined:

Participant Analysis Set	Description
Enrolled	All participants who sign the ICD.
Full analysis set (FAS)	All participants who are randomly assigned to study intervention and receive all 3 doses of study intervention, and complete at least 7 days of GC. Participants will be analyzed according to the intervention they are randomized.
Per protocol set (PPS)	The PPS will include all participants from the FAS who complete all 14 days of GC and biopsies, and without major protocol violations that might affect the evaluation of the effect of study intervention on the primary endpoint. The PPS will be used in sensitivity analyses of the primary and secondary endpoints. Specific reasons for warranting exclusion from this population will be documented prior to database lock.
Safety analysis set	All participants who receive any portion of study intervention. Participants will be analyzed according to the intervention they actually received.
PK analysis set	All participants who receive any portion of study intervention and have at least one post-dose concentration value.

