3. ANALYSIS SETS

For purposes of analysis, the following analysis sets are defined:

Analysis Set	Description
Enrolled	All participants who sign the ICD.
Biomarker Analysis Set (BAS)	All participants who are randomly assigned to study intervention, receive any portion of study intervention, and have completed the GC on Day 15, without prohibited medications. Participants will be analyzed according to the intervention they are randomized.
Full analysis set (FAS)	All participants who are randomly assigned to study intervention, receive all 3 doses of study intervention, and complete at least 7 days of the 2-week GC without prohibited medications. Participants will be analyzed according to the intervention they are randomized.

Analysis Set	Description
Per protocol set (PPS)	The PPS will include all participants from the FAS who complete all 14 days of the 2-week GC and biopsies, and without major protocol violations that might affect the evaluation of the effect of study intervention on the primary endpoint. The PPS will be used in sensitivity analyses of the primary and secondary endpoints. Specific reasons for warranting exclusion from this population will be documented prior to database lock.
Safety analysis set (SAS)	All participants who receive any portion of study intervention. Participants will be analyzed according to the intervention they actually received.
PK analysis set (PKAS)	All participants who receive any portion of study intervention and have at least one concentration value.

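### A challenge day on which the full 9 g is eaten slowly does not count as completed; 8 or more such days of 14 cost the second biopsy and FAS membership

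*Protocol*

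**What the plan says.** The primary objective concerns duodenal histology "as measured by changes in villus-height:crypt depth (Vh:Cd) ratio after a 2-week GC". The challenge runs for 14 days: Day 15 in clinic, then 13 days at home.

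Protocol 8.2.1 gives the only definition of a completed challenge in either document: "Completion of the GC is defined as consumption of the entirety of the 9g GC within approximately 15 minutes". It covers both settings, since the text that follows it has Day 15 observed on site and completion on the remaining days entered by the participant in the eDiary.

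Completion then acts as a gate in four places:

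- **Second biopsy.** Protocol 8.2.1: "Only participants who have completed at least 7 days of GC should undergo the second EGD with biopsy". The Schedule of Assessments repeats this: "Only participants who have completed all 3 doses of study intervention and at least 7 days of GC should undergo EGD".
- **FAS, which carries the primary ANCOVA.** Protocol 9.3 requires participants to "receive all 3 doses of study intervention, and complete at least 7 days of GC"; SAP Section 3 has "receive all 3 doses of study intervention, and complete at least 7 days of the 2-week GC without prohibited medications".
- **PPS.** All 14 days completed, plus biopsies (Protocol 8.2.1 and 9.3, SAP Section 3).
- **Biomarker Analysis Set (BAS), used for IL-2.** Day 15 challenge completed (SAP Section 3).

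Missing efficacy values are not imputed (Protocol 9.4.1.2, SAP 4.3).

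**The concern.** A limit on eating time makes sense on Day 15. The IL-2 sample is drawn 4 hours (± 15 minutes) after the challenge, so a drawn-out intake would blur the sampling time. The Day 29 biopsy instead reflects two weeks of cumulative exposure, and neither document says why the pace of intake on Days 16 to 28 should decide who is biopsied.

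The consequence would be permanent. A participant without a second biopsy has no Day 29 value. The supplementary analysis on the Safety Analysis Set (SAP 5.1.2) cannot recover it, because it fits the same ANCOVA to observed values.

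There is also a selection question. Nausea, vomiting and abdominal pain are expected effects of the challenge (Protocol 2.3.1), and the effect of KAN-101 on symptoms during the challenge is an exploratory objective. If symptoms slow intake, a rule based on pace conditions the primary analysis on something that treatment may influence after randomisation.

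**Working it through.** **Step 1. The plan's own power figures.** Inputs from Protocol 9.6: difference d = 0.50, SD = 0.5, 26 per arm, two-sided 5%. Two-sample t test, noncentrality d / (SD × √(1/n1 + 1/n2)), df = n1 + n2 − 2.

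- 26 vs 26: 0.5 / (0.5 × √(2/26)) = 3.61 on 50 df, power 94.2% (94.1% at the SAP's final level of 0.049). Stated: about 94%.
- Dropout of 20% and 40%: 26 × 0.8 = 20.8 and 26 × 0.6 = 15.6, power 82.7%; with whole numbers, 83.4% at 21 vs 16 and 82.0% at 21 vs 15. Stated: 82%.

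Both figures reproduce.

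**Step 2. Day count.** Let s be the number of days on which all 9 g is eaten but the time limit is clearly exceeded. Completed days = 14 − s. The second biopsy and the FAS need 14 − s ≥ 7, that is s ≤ 7.

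| Slow days s | Completed days | Second biopsy and FAS | PPS |
|---|---|---|---|
| 0 | 14 | kept | kept |
| 1 to 7 | 13 to 7 | kept | lost |
| 8 to 14 | 6 to 0 | lost | lost |

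BAS membership depends on Day 15 alone. A participant who is on time on Day 15 and slow on all 13 home days has 1 completed day: in the BAS, but with no second biopsy and outside the FAS.

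**Step 3. How often this could happen (assumption).** The documents give no rate. Suppose each day is slow independently with probability q. The chance of fewer than 7 completed days is P(Binomial(14, 1 − q) ≤ 6):

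| q | 0.2 | 0.3 | 0.4 | 0.5 | 0.6 |
|---|---|---|---|---|---|
| P(loss of biopsy and FAS) | 0.2% | 3.1% | 15.0% | 39.5% | 69.2% |

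Occasional slow days hardly affect the FAS; habitual slowness does. The PPS is far more sensitive: at q = 0.1 the chance of all 14 days on time is 0.9^14 = 22.9%.

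**Step 4. Power if participants are lost (numbers assumed, equal per arm).** Same formula as Step 1.

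| Lost per arm | 0 | 1 | 2 | 4 |
|---|---|---|---|---|
| From 26 vs 26 | 94.2% | 93.4% | 92.4% | 90.0% |
| From 21 vs 16 | 83.4% | 81.1% | 78.5% | 72.5% |

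The second row treats these losses as additional to the planned dropout. If the plan's 30% already includes them, they add nothing.

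**Step 5. Exposure.** Full intake on every day is 14 × 9 g = 126 g. The minimum for the FAS is 7 × 9 g = 63 g. Read literally, 126 g eaten slowly is not evaluable, while 63 g eaten on time is.

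**The case against.** The strongest reply is that the plan shows an ambiguity and not a demonstrated exclusion. The limit is approximate. At-home completion is self-entered, and neither document says that eating time is recorded; SAP 5.4.4 summarises days completed and mixture type, not duration. The FAS wording does not cross-refer to 8.2.1. In practice a slow but full day may simply be entered as complete. The challenge may be mixed with a drink and symptomatic antiemetics are permitted, so many slow days may be rare. All of this stands as a limit on the likely size. It does not remove the problem: 8.2.1 holds the only definition, and a condition that decides biopsy and FAS membership is either applied as written or left to individual reading with no means of audit.

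A reader might infer three stronger things that the documents do not support.

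- That any slow eater loses the biopsy. Up to 7 slow days leave biopsy and FAS intact.
- That the losses fall mainly on placebo. The 20%/40% split in Protocol 9.6 is given as an example and is not linked to eating speed. Protocol 2.2.3 reports GI adverse events in more participants on drug than on placebo in the first-in-human study.
- That the time limit alone explains the 63 g versus 126 g contrast. Half of it comes from the 7-day threshold: 63 g would remain sufficient for the FAS without any time limit, and a participant who stops on the sixth day would still be lost.

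A further fair point is that 8.2.1 standardises each challenge as one intake after a fast of at least 6 hours, at home as well. A rule that ignored time altogether would admit portions spread over the day. The remedy has to respect that.

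**Conclusion.** The point holds in a limited form. A definition suited to the Day 15 IL-2 test also decides who contributes to the primary histology endpoint. Read literally, it removes participants with full gluten exposure once 8 or more of their 14 days exceed about 15 minutes. One slow day is enough to lose the PPS, and a slow Day 15 loses the BAS.

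This rests on two readings: that completing a day in the biopsy rule and the FAS carries the 8.2.1 meaning, which is the natural reading because no other definition exists; and that sites apply the limit at home. The number affected is unknown. One or two losses per arm from 26 would cost about 1 to 2 points of power; on top of the plan's dropout case, about 2 to 5 points. Selection on a post-randomisation outcome is possible, but its direction by arm is not established. The change is worth making because the lost endpoint cannot be recovered and the correction is cheap.

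**What to change.** Separate the two uses of completion.

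- Keep the condition of approximately 15 minutes for the supervised Day 15 challenge, the BAS and, if the sponsor wishes, the PPS.
- For the 7-day count that decides the second EGD and the FAS, count an at-home day when the eDiary documents that the entire 9 g was eaten as that day's single post-fast challenge, even if it took longer than about 15 minutes.
- Use the same wording in Protocol 8.2.1, the Schedule of Assessments and Protocol 9.3, and in SAP Section 3.
- Have the eDiary record, for each day, whether intake was full and whether the time was exceeded, so that membership of each set can be checked.

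The gluten amount, fasting rule and procedures stay as they are. Some participants would have the already planned second EGD who would otherwise have missed it. The cost is an amendment to protocol and SAP wording, an added eDiary item, and slightly less uniform speed of intake in the FAS. New wording cannot restore a biopsy that was not taken; for participants already past Day 29, the SAP should state how completed days were counted.
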